6.5 STUDY INTERVENTION COMPLIANCE

The investigator will maintain accurate records of receipt of all the study medications, including dates of receipt. In addition, accurate records will be kept regarding when and how much study treatment is dispensed and used by each subject in the study. Reasons for deviation from the expected dispensing regimen must also be recorded. At completion of the study, to satisfy regulatory requirements regarding drug accountability, all unused cabozantinib will be reconciled and destroyed in accordance with applicable state and federal regulations.

6.6 CONCOMITANT THERAPY

All treatments that the investigator considers necessary for a subject's welfare may be administered at the discretion of the investigator in keeping with the community standards of medical care. All concomitant medication will be recorded on the case report form (CRF) including all prescription, over the counter (OTC), herbal supplements, and IV medications and fluids. If changes occur during the trial period, documentation of drug dosage, frequency, route, and date will also be included on the CRF.

Palliative and supportive care is permitted during the course of the trial for underlying medical conditions and management of symptoms. Surgery for tumor control or symptom management is not permitted during the study. Palliative radiotherapy is permitted to a single lesion if considered medically necessary by the treating physician as long as the lesion is NOT a RECIST 1.1 defined target lesion and is radiation is NOT administered for tumor control. Cabozantinib should be held during the course of palliative radiotherapy and

resumed 1 week after completion of palliative radiotherapy. The specifics of the radiation treatment, including the location, will be recorded. All concomitant medications received within 30 days before the first dose of trial treatment through 30 days post last dose or until new treatment is started, whichever occurs first should be recorded.

6.6.1 RESCUE MEDICINE

Subjects should receive appropriate supportive care measures as deemed necessary by the treating investigator including but not limited to the items outlined below.

Diarrhea: Subjects should be carefully monitored for signs and symptoms of enterocolitis (such as diarrhea, abdominal pain, blood or mucus in stool, with or without fever) and of bowel perforation (such as peritoneal signs and ileus). In symptomatic subjects, infectious etiologies should be ruled out, and if symptoms are persistent and/or severe, endoscopic evaluation should be considered. All subjects who experience diarrhea should be advised to drink liberal quantities of clear fluids. If sufficient oral fluid intake is not feasible, fluid and electrolytes should be substituted via IV infusion.

Nausea/vomiting: Administration of prophylaxis for nausea and vomiting should be administered per institutional guidelines and local standard practices for the standard of care chemotherapies offered for the control arm. For pembrolizumab, the therapy is considered to be of low to moderate emetogenic potential. Consideration for chemo induced nausea and vomiting prophylaxis should be given in subsequent cycles of the administration according to standard institutional practice and should not be routinely administered prior to the initial trial treatment of pembrolizumab. Subjects should be strongly encouraged to maintain liberal oral fluid intake.

Anemia: Erythropoietic stimulating agents (e.g., epoetin alfa and darbepoetin alfa) should not be used based on a report of increased risk of tumor recurrence/progression associated with erythropoietin.

Neutropenia: Prophylactic use of colony-stimulating factors including Granulocyte Colony-Stimulating Factor (G-CSF), pegylated G-CSF or Granulocyte Macrophage Colony-Stimulating Factor GM CSF is not allowed in this trial. Therapeutic use of G-CSF is allowed in subjects with Grade 3-4 febrile neutropenia. Consider a potential immunologic etiology.

Thrombocytopenia: Transfusion of platelets may be used if clinically indicated. ITP should be ruled out before initiation of platelet transfusion.

Anti-infectives: Subjects with a documented infectious complication should receive oral or IV antibiotics or other anti-infective agents as considered appropriate by the treating Investigator for a given infectious condition, according to standard institutional practice.

Events of Clinical Interest with a potential immunologic etiology (ECI): Please see the separate guidance document in the administrative binder regarding identification, evaluation and management of adverse experiences of a potential immunologic etiology. Depending on the type and severity of an ECI, oral or intravenous treatment with a corticosteroid should be

considered, in addition to appropriate symptomatic treatment of a given condition.

6.6.2 SUPPORTIVE CARE GUIDELINES

IMMUNE-RELATED ADVERSE EVENTS (IRAE)

Adverse events (both non-serious and serious) associated with drug exposure and consistent with an immune phenomenon may represent an immunologic etiology. These immune related adverse events (irAEs) may be predicted based on the nature of the pembrolizumab compound, its mechanism of action, and reported experience with immunotherapies that have a similar mechanism of action. An irAE can occur shortly after the first dose or several months after the last dose of treatment. Attention should be paid to AEs that may be suggestive of potential irAEs.

Table 10: Pembrolizumab Infusion Reaction Treatment Guidelines

NCI CTCAE Grade	Treatment	Premedication at Subsequent Dosing
Grade 1 Mild reaction; infusion interruption not indicated; intervention not indicated	Increase monitoring of vital signs as medically indicated until the subject is deemed medically stable in the opinion of the investigator	None
Grade 2 Requires infusion interruption but responds	Stop Infusion.	Subject may be premedicated 1.5h (\pm 30-minutes) prior to

promptly to symptomatic treatment (e.g., antihistamines, NSAIDS, narcotics, IV fluids); prophylactic medications indicated for <=24 hrs
	
Additional appropriate medical therapy may include but is not limited to: IV fluids Antihistamines NSAIDS Acetaminophen Narcotics Increase monitoring of vital signs as medically indicated until the subject is deemed medically stable in the opinion of the investigator. If symptoms resolve within one hour of stopping drug infusion, the infusion may be restarted at 50% of the original infusion rate (e.g. from 100 mL/hr to 50 mL/hr). Otherwise dosing will be held until symptoms resolve and the subject should be premedicated for the next scheduled dose. Subjects who develop Grade 2 toxicity despite adequate premedication should be permanently discontinued from further trial treatment administration.
	
infusion of pembrolizumab with: Diphenhydramine 50 mg po (or equivalent dose of antihistamine). Acetaminophen 500-1000 mg po (or equivalent dose of analgesic).


Grades 3 or 4 Grade 3: Prolonged (i.e., not rapidly responsive to symptomatic medication and/or brief interruption of infusion); recurrence of symptoms following initial improvement; hospitalization indicated for other clinical sequelae (e.g., renal impairment, pulmonary infiltrates)
 
Grade 4: Life-threatening; pressor or ventilatory support indicated
	
Stop Infusion. Additional appropriate medical therapy may include but is not limited to: IV fluids Antihistamines NSAIDS Acetaminophen Narcotics Oxygen Pressors Corticosteroids Epinephrine Increase monitoring of vital signs as medically indicated until the subject is deemed medically stable in the opinion of the investigator. Hospitalization may be indicated. Subject is permanently discontinued from further trial treatment administration.
	
No subsequent dosing

Appropriate resuscitation equipment should be available at the bedside and a physician readily available during the period of drug administration.
For Further information, please refer to the Common Terminology Criteria for Adverse Events v4.0 (CTCAE) at <http://ctep.cancer.gov>

6.6.3 ALLOWED THERAPY

- Antiemetics and antidiarrheal medications are allowed prophylactically according to standard clinical practice if clinically indicated.
- Granulocyte colony-stimulating factors (G-CSF or GM-CSF) are allowed if used per clinical guidelines (eg, ASCO or ESMO guidelines).
- Bisphosphonates can be used to control bone loss or hypocalcemia if the benefit outweighs the risk per the investigator's discretion.

Note: osteonecrosis of the jaw has been reported in subjects using bisphosphonates. Oral examinations are recommended at screening to determine eligibility and periodically during the study. In addition, subjects should be advised regarding oral hygiene practice and to quickly report symptoms to the investigator. Frequent monitoring for potentially overlapping toxicities with study treatment is recommended.

- Transfusions and hormone replacement should be utilized as indicated by standard clinical practice.
- Individualized anticoagulation therapy with heparin is allowed if it can be provided safely and effectively under the following circumstances:
 - *Low dose heparins for prophylactic use* are allowed if clinically indicated and the benefit outweighs the risk per the investigator's discretion.
 - *Therapeutic doses of LMWH at the time of the first dose of study treatment* are allowed if the subject has no evidence of brain metastasis, has been on a stable dose of LMWH for at least 6 weeks, and has had no complications from a thromboembolic event or the anticoagulation regimen.
 - *Therapeutic doses of LMWH after first dose of study treatment* are allowed if clinically indicated (eg, for the treatment of deep venous thrombosis), and the benefit outweighs the risk per the investigator's discretion. For management of thromboembolic complications while on study, refer to Section 6.2.
 - Accepted clinical guidelines regarding appropriate management while receiving anticoagulation therapy with heparins must be followed. This includes, but is not limited to, subject education regarding potential adverse drug reactions, monitoring laboratory parameters, dose adjustments (eg, due to kidney dysfunction).

For restrictions on oral anticoagulants see 5.2.

6.6.4 PROHIBITED OR RESTRICTED THERAPY

The following therapies are prohibited until study treatment has been permanently discontinued:

- Any investigational agent or investigational medical device.
- Oral anticoagulants (eg, warfarin or other coumarin-related agents, direct thrombin or direct FXa inhibitors, or antiplatelet agents such as clopidogrel, or chronic use of aspirin above low dose levels for cardioprotection per local applicable guidelines).
- Any non-protocol systemic anticancer treatment (eg, chemotherapy, immunotherapy, radionuclides, drugs or herbal products used specifically for the treatment of the cancer under investigation).

The following therapies should be avoided until study treatment has been permanently discontinued or until otherwise specified:

- Local anticancer treatment including palliative radiation, ablation, embolization, or surgery with impact on tumor lesions should not be performed until radiographic progression per RECIST 1.1 has been established.
- Erythropoietic stimulating agents (eg, epoetin alfa and darbepoetin alfa) should not be used based on a report of increased risk of tumor recurrence/progression associated with erythropoietin (Wright et al 2007).
- Concomitant medications that are known to prolong the QTc interval should be avoided in subjects who receive cabozantinib until they have permanently discontinued cabozantinib treatment (refer to <http://www.qtdrugs.org> for a list of drugs which have the potential to prolong the QTc interval).

Chronic co-administration of cabozantinib with strong inducers of the CYP3A4 family (eg, phenytoin, carbamazepine, rifampin, rifabutin, rifapentine, phenobarbital, and St. John's Wort) may significantly decrease cabozantinib concentrations and should be avoided. Selection of alternate concomitant medications with no or minimal CYP3A4 enzyme induction potential is recommended.

- Caution must be used when discontinuing treatment with a strong CYP3A4 inducer in a subject who has been concurrently receiving a stable dose of cabozantinib, as this could significantly increase the exposure to cabozantinib.
- Co-administration of cabozantinib with strong inhibitors of the CYP3A4 family (eg, boceprevir, conivaptan, posaconazole, ketoconazole, itraconazole, clarithromycin, atazanavir, indinavir, nefazodone, neflunavir, saquinavir, ritonavir, lopinavir, telaprevir, telithromycin, and voriconazole) may increase cabozantinib concentrations and should be avoided. Grapefruit, star fruit, and Seville oranges may also increase plasma concentrations of cabozantinib and should be avoided.

6.6.5 POTENTIAL DRUG INTERACTIONS WITH CABOZANTINIB

Cytochrome P450: Data from a clinical drug interaction study (Study XL184-008) show that clinically relevant steady-state concentrations of cabozantinib appear to have no marked effect on the area under the plasma concentration-vs-time curve (AUC) of co-administered rosiglitazone, a CYP2C8 substrate. Therefore, cabozantinib is not anticipated to markedly inhibit CYP2C8 in the clinic, and by inference, is not anticipated to markedly inhibit other CYP450 isozymes that have lower [I]/Ki values compared to CYP2C8 (ie, CYP2C9, CYP2C19, CYP2D6, CYP1A2, and CYP3A4). In vitro data indicate that cabozantinib is unlikely to induce cytochrome P450 enzymes, except for possible induction of CYP1A1 at high cabozantinib concentrations (30 μ M).

Cabozantinib is a CYP3A4 substrate and a weak substrate for CYP2C9 (but not a CYP2D6, CYP2C8, CYP2C19, CYP2B6, or CYP1A2 substrate), based on data from in vitro studies. Results from a clinical pharmacology study, XL184-006, showed that concurrent administration of cabozantinib with the strong CYP3A4 inducer, rifampin, resulted in an approximately 77% reduction in cabozantinib exposure (AUC values) after a single dose of cabozantinib in healthy volunteers. Chronic co-administration of cabozantinib with strong inducers of the CYP3A4 family (eg, phenytoin, carbamazepine, rifampin, rifabutin, rifapentine, phenobarbital, and St. John's Wort) may significantly decrease cabozantinib concentrations. The chronic use of strong CYP3A4 inducers should be avoided. Other drugs that induce CYP3A4 should be used with caution because these drugs have the potential to decrease exposure (AUC) to cabozantinib. Selection of alternate concomitant medications with no or minimal CYP3A4 enzyme induction potential is recommended.

Results from a clinical pharmacology study, XL184-007, showed that concurrent administration of cabozantinib with the strong CYP3A4 inhibitor, ketoconazole, resulted in a 38% increase in the cabozantinib exposure (AUC values) after a single dose of cabozantinib in healthy volunteers. Co-administration of cabozantinib with strong inhibitors of the CYP3A4 family (eg, boceprevir, conivaptan, posaconazole, ketoconazole, itraconazole, clarithromycin, atazanavir, indinavir, nefazodone, neflifavir, saquinavir, ritonavir, lopinavir, telaprevir, telithromycin, and voriconazole) may increase cabozantinib concentrations. Grapefruit, star fruit and Seville oranges may also increase plasma concentrations of cabozantinib and should be avoided. Strong CYP3A4 inhibitors should be avoided and other drugs that inhibit CYP3A4 should be used with caution because these drugs have the potential to increase exposure (AUC) to cabozantinib. Selection of alternate concomitant medications with no or minimal CYP3A4 enzyme inhibition potential is recommended.

Please refer to the drug interaction tables at the following websites for lists of substrates, inducers, and inhibitors of selected CYP450 isozyme pathways:

<Http://medicine.iupui.edu/clinpharm/ddis/table.aspx>

<http://www.fda.gov/Drugs/DevelopmentApprovalProcess/DevelopmentResources/DrugInteractionsLabeling/ucm080499.htm>).

Protein Binding: Cabozantinib is highly bound ($\geq 99.7\%$) to human plasma proteins. Therefore, highly protein bound drugs should be used with caution with cabozantinib because there is a potential displacement interaction that could increase free concentrations of cabozantinib and/or a co-administered highly protein-bound drug (and a corresponding increase in pharmacologic effect).

Other Interactions: Food may increase exposure levels of cabozantinib by 57%, fasting recommendations should be followed. In vitro data suggest that cabozantinib is unlikely to be a substrate for P-glycoprotein, but it does appear to have the potential to inhibit the P-glycoprotein transport activity. Therefore, cabozantinib may have the potential to increase plasma concentrations of co-administered substrates of P-glycoprotein. Additional details related to these overall conclusions can be found in the investigator brochure.

Administration of the proton pump inhibitor (PPI) esomeprazole resulted in no clinically-relevant effect on cabozantinib plasma PK in healthy volunteers. Therefore, concomitant use of gastric pH modifying agents (ie, PPIs, H₂ receptor antagonists, and antacids) is not contraindicated in subjects administered cabozantinib.

Additional details regarding potential drug interactions with cabozantinib can be found in the investigator brochure.

Cabozantinib was shown to be a substrate of drug transporter MRP2 in an in vitro assay. Administration of MRP2 inhibitors to subjects may result in increases in cabozantinib plasma concentrations.

7 STUDY INTERVENTION DISCONTINUATION AND PARTICIPANT DISCONTINUATION/WITHDRAWAL

7.1 DISCONTINUATION OF STUDY INTERVENTION

Treatment with cabozantinib and pembrolizumab may continue until one of the following events occurs:

- Documented disease progression
- Intercurrent illness that prevents further administration of treatment
- Unacceptable adverse experiences.
- Need for >2 dose delays due to the same toxicity as per the dose modification guidelines described.

- Patient withdraws consent
- If in the opinion of the Investigator, a change or temporal or permanent discontinuation of therapy would be in the best interest of the patient. The SPONSOR should be included in this decision.
- Patient is lost to follow-up
- Pregnancy in patient

7.2 PARTICIPANT DISCONTINUATION/WITHDRAWAL FROM THE STUDY

Patients may withdraw from the study at any time. Patients who discontinue early should return within 30 days (+/- 7 days) of the last dose of the study drugs for a follow-up evaluation. Any assessments listed for the final visit in Table will be performed at that time.

In addition, any of the following conditions require the withdrawal of the subject from study treatment:

- An AE or intercurrent illness that in the opinion of the investigator warrants the subject's withdrawal from treatment
 - The investigator believes it is not in the best interest of the subject to continue on study
- Necessity for treatment with other investigational drug or other anticancer medications prohibited by protocol
- Noncompliance with the protocol schedule
- Participation in another clinical study using anticancer agent(s)
- Request by regulatory agencies for termination of treatment of an individual subject or all subjects under this protocol
- Sexually active subjects who refuse to use medically accepted barrier methods of contraception (eg, male condom, female condom) during the course of the study and for 3 months following discontinuation of study treatment
- Women who become pregnant or are breast feeding
- Inability to tolerate cabozantinib
- Cabozantinib treatment delays > 6 weeks unless the subject was unequivocally benefitting from cabozantinib treatment
- Progressive disease (PD) as determined by the investigator. However, patients who continue to derive clinical benefit from cabozantinib and pembrolizumab as judged by the investigator may continue therapy despite radiographic progression of the disease.

The reason for study treatment discontinuation will be documented. For subjects who discontinue or are withdrawn from study treatment, every effort must be made to undertake protocol-specified follow-up procedures and end-of-treatment assessments, if possible, unless consent to participate in the study is also withdrawn.

If a subject fails to return for the protocol-defined visits, an effort must be made to determine the reason. If the subject cannot be reached by telephone, at the minimum a registered letter

should be sent to the subject (or the subject's legal guardian) requesting contact with the clinic. If a subject is discontinued from study treatment because of an AE considered to be related to study treatment and the event is ongoing 30 days after the last dose of study treatment, the event must be followed until resolution or determination by the investigator that the event has become stable or irreversible.

If a subject withdraws consent to participate in the study, the reason for withdrawal will be documented, no further study procedures or assessments will be performed, and no further study data will be collected for this subject, other than the determination of survival status from public records such as government vital statistics or obituaries.

Patients that withdraw from study treatment (but not their consent for follow-up) for reasons other than progression will continue to have scans per study calendar until PD is noted.

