- k) **Drug Interactions**: Avoid administration of cabozantinib with agents that are strong CYP3A4 inducers or inhibitors.
- l) **Hepatic Impairment**: Cabozantinib is not recommended for use in patients with moderate or severe hepatic impairment.
- m) **Embryo-fetal Toxicity**: Cabozantinib can cause fetal harm when administered to a pregnant woman. Cabozantinib was embryo-lethal in rats at exposures below the recommended human dose, with increased incidences of skeletal variations in rats and visceral variations and malformations in rabbits.

2.3.1.2: PEMBROLIZUMAB

- a) **Immune-Mediated Pneumonitis**: Pembrolizumab can cause immune-mediated pneumonitis, including fatal cases. Pneumonitis occurred in 94 (3.4%) of 2799 patients receiving pembrolizumab, including Grade 1 (0.8%), Grade 2 (1.3%), Grade 3 (0.9%), Grade 4 (0.3%), and Grade 5 (0.1%) pneumonitis. The median time to onset was 3.3 months (range: 2 days to 19.3 months), and the median duration was 1.5 months (range: 1 day to 17.2+ months). Sixty-three (67%) of the 94 patients received systemic corticosteroids, with 50 of the 63 receiving high-dose corticosteroids for a median duration of 8 days (range: 1 day to 10.1 months) followed by a corticosteroid taper. Pneumonitis occurred more frequently in patients with a history of prior thoracic radiation (6.9%) than in patients who did not receive prior thoracic radiation (2.9%). Pneumonitis led to discontinuation of pembrolizumab in 36 (1.3%) patients. Pneumonitis resolved in 55 (59%) of the 94 patients.
- b) **Immune-Mediated Colitis**: Pembrolizumab can cause immune-mediated colitis. Monitor patients for signs and symptoms of colitis. Colitis occurred in 48 (1.7%) of 2799 patients receiving pembrolizumab, including Grade 2 (0.4%), Grade 3 (1.1%), and Grade 4 (<0.1%) colitis. The median time to onset was 3.5 months (range: 10 days to 16.2 months), and the median duration was 1.3 months (range: 1 day to 8.7+ months). Thirty-three (69%) of the 48 patients received systemic corticosteroids, with 27 of the 33 requiring high-dose corticosteroids for a median duration of 7 days (range: 1 day to 5.3 months) followed by a corticosteroid taper. Colitis led to discontinuation of pembrolizumab in 15 (0.5%) patients. Colitis resolved in 41 (85%) of the 48 patients.

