5 STUDY POPULATION

5.1 INCLUSION CRITERIA

A patient must meet all of the following criteria to be eligible for enrollment (defined as receiving the first trial treatment) in the trial:

1. Histologically or cytologically confirmed unresectable in-transit (stage IIIc) or metastatic (stage IV) melanoma.
2. Must have at least 1 lesion that qualifies as a measurable (target) lesion per RECIST v1.1
3. Subjects must be willing to have blood draws for future biomarker testing as outlined in Section 11.9.
4. The subject has an ECOG performance score of ≤ 2 However; the phase 1b part will include only ECOG performance of 0-1 and life expectancy of >12 weeks
5. Aged 18 years and older.
6. The subject should not have received any treatment for advanced melanoma, EXCEPT, BRAF and/or MEK inhibitor. (2 week washout)
7. The subjects who have received adjuvant therapy including anti- PD-1 can be included in the study, if the last dose of the adjuvant treatment was ≥ 6 months prior to developing metastatic relapse.
8. The subject is capable of understanding and complying with the protocol requirements and has signed the informed consent document.
9. Female patients of childbearing potential must have a negative urine or serum pregnancy test within 72 hours prior to taking the first dose of study medication, if. If the urine test is positive or cannot be confirmed as negative, then a serum test is required which must be negative for the patient to enroll. Women of childbearing potential (WOCBP) must be willing to use 2 medically acceptable methods of contraceptive from Day 1 through 120 days after the last dose of trial treatment. The 2 medically acceptable birth control methods can be either 2 barrier methods or a barrier method plus a hormonal method to prevent pregnancy. The following are considered adequate barrier methods of contraception: diaphragm, condom (by the partner), copper intrauterine device, sponge, or spermicide as per local regulations or guidelines. Appropriate hormonal contraceptives will include any registered and marketed contraceptive agent that contains an estrogen and/or a progestational agent (including oral, subcutaneous, intrauterine, or intramuscular agents). Male patients of reproductive potential must agree to use an adequate method of contraception from Day 1 through 120 days after the last dose of trial treatment. Abstinence is acceptable if this is the usual lifestyle and preferred contraception for the patient.

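### Sections 5.1 and 7.2 state the post-treatment contraception precaution with different durations, starting points, methods and covered participants, so a participant can comply with 5.1 and still meet a mandatory withdrawal condition in 7.2

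*Combined protocol and SAP*

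**What the plan says.** Section 5.1, inclusion criterion 9, has two parts. Women of childbearing potential "must be willing to use 2 medically acceptable methods of contraceptive from Day 1 through 120 days after the last dose of trial treatment". The two methods may be two barrier methods, or one barrier and one hormonal method. For men of reproductive potential, the criterion is that they "must agree to use an adequate method of contraception from Day 1 through 120 days after the last dose of trial treatment". It also accepts abstinence where this is the participant's usual and preferred practice.

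Section 7.2 lists conditions under the statement that "any of the following conditions require the withdrawal of the subject from study treatment". One of them is "Sexually active subjects who refuse to use medically accepted barrier methods of contraception (eg, male condom, female condom"), with the period given as the course of the study and then "for 3 months following discontinuation of study treatment".

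The reason for the precaution is in section 2.3.1. For one drug it states that "Cabozantinib can cause fetal harm when administered to a pregnant woman", and it makes the corresponding statement for pembrolizumab on the basis of its mechanism of action.

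**The concern.** Two operative sections describe one precaution and disagree on four things: how long it lasts after treatment, the event from which that time is counted, which methods satisfy it, and whom it covers. Neither is amendment-log or superseded text, and no sentence assigns one period to one drug, sex or group and the other to another.

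Two things are at stake. First, staff who take the post-treatment period from 7.2 may state a different period from the one in the eligibility criterion, for drugs that the protocol says can harm a fetus. Second, the 7.2 list is mandatory. A mismatch in methods or scope therefore bears on who may stay on study treatment, as well as on a date.

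**Working it through.** The plan gives no figure to reproduce here. The check is a comparison of the two texts plus calendar arithmetic.

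**Side by side**

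| Item | 5.1, criterion 9 | 7.2, withdrawal condition |
|---|---|---|
| Period after treatment | 120 days | 3 months |
| Counted from | last dose of trial treatment | discontinuation of study treatment |
| Women | two methods, at least one a barrier | barrier methods |
| Men | an adequate method | barrier methods |
| Who is covered | childbearing or reproductive potential | any sexually active subject |

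**Duration, same start day.** Adding three calendar months to every date from 2019 to 2024 gives 89 to 92 days.
- Smallest gap: 120 − 92 = 28 days.
- Largest gap: 120 − 89 = 31 days.

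Three months is never 120 days, so rounding does not explain the difference.

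**Duration, different start days.** Let d be the number of days from the last dose to the date recorded as discontinuation. Counted from the last dose, the 7.2 period ends at d + (89 to 92), and the gap is 120 − d − (89 to 92).
- d = 0: the 7.2 period ends 28 to 31 days earlier than the 5.1 period.
- d of 28 to 31: the two end dates coincide.
- d = 42: the 7.2 period ends at day 131 to 134, which is 11 to 14 days later than the 5.1 period.

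The value d = 42 is an illustration. It assumes that both drugs have been held for 6 weeks and that discontinuation is dated at the decision to stop. Section 6.1.2.3 and section 7.2 use 6 weeks as the limit on cabozantinib interruption, with exceptions. The serious adverse event sections (8.3.6 and 11.7.1) count time from the decision to discontinue. Section 7.2 does not say which date it means.

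**Methods and scope.** Two participants show the conflict without any arithmetic.
- A man of reproductive potential uses an adequate non-barrier method and declines a barrier method. He satisfies criterion 9 and meets the 7.2 condition.
- A sexually active participant without reproductive potential declines barrier methods. Criterion 9 places no contraception duty on this person, but the 7.2 condition as worded applies.

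**Scheduled contacts.** Under the study calendar (1.3), the end-of-treatment visit is 30 days after the last dose, give or take 7, or earlier if another treatment starts. Follow-up is then every 3 months from that visit. For a visit at day 30, the first later contact falls at about 30 + 89 = 119 to 30 + 92 = 122 days. With d = 0 that is after the 7.2 period has ended. This contact is for survival and progression and, under 8.3.4.2, may be by telephone. A wrong period given at the final visit might therefore not be noticed before it had run out.

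**The case against.** The best reply is that 7.2 is a trigger for withdrawal from treatment and gives no instruction about when contraception may stop. A reader might infer that it ends the precaution early, or that it enforces the shorter period. The text does not support either reading. The condition releases nobody from criterion 9, and with a common start day a participant who keeps to 120 days has also covered 3 months. Someone already off treatment cannot be withdrawn from it, so the post-treatment part of the condition takes effect only when a participant still on treatment declares a future refusal. This stands. What remains is that 7.2 states a second post-treatment duration for the same precaution, and staff may read it as the period.

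A reader might also infer that participants are given two end dates. That cannot be shown, because the consent pages are not in the copy reviewed. The conflict is established only for the protocol text that staff use.

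On methods, the conflict is narrower for women than it may look. Every option in 5.1 for women already includes a barrier method, so the difference there is that 7.2 does not mention the second method. The abstinence allowance does not conflict either, since 7.2 applies only to sexually active subjects. The conflict for men, and for participants without reproductive potential, is unaffected by these points.

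Finally, eligibility already commits participants to the 120-day period, and section 5.2 excludes people expecting to conceive or father children within the projected duration of the study. Both lower the practical risk, but neither reconciles the two sections.

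**Conclusion.** The inconsistency is real and limited. Sections 5.1 and 7.2 disagree on duration, starting point, methods and scope, and nothing in the document resolves the disagreement. The 28 to 31 day difference rests on both clocks starting on the same day. It is not a fixed shortfall for each participant, because the undefined discontinuation date can remove or reverse it. The conflict in methods and scope needs no such assumption: it follows from the wording, read literally. This is a consistency and participant-safety point of modest weight. It has no bearing on the response-rate endpoint, the type I error, the power or the two-stage rule.

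**What to change.** Reconcile criterion 9 in 5.1 with the contraception condition in 7.2 so that both state:
- one post-treatment duration;
- one starting point, defined so that an interruption before the decision to stop does not leave it ambiguous, and covering the case where the two drugs stop on different days;
- one set of acceptable methods for each sex;
- one covered population.

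The clinical team decides the content of each; this review takes no view on which is right. A simple way is to have 7.2 and 5.1 rely on a single statement by cross-reference. The consent form should then be checked against the reconciled text. The cost is about one sentence in the protocol plus the consent check, with no change to the sample size, the analyses or the assessment schedule.
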